AVANCE-Houston Building Futures Program Evaluation

Study Protocol

3/9/2023

Clinicaltrials.gov ID: NCT05293145

Evaluation of AVANCE-Houston Building Futures Project in Harris County

I. Research Question(s)

A. Background

Early relationships can both positively and negatively influence professional, peer, and romantic relationships later in life, and research indicates that adolescents often do not have the necessary knowledge and skills to recognize and develop healthy relationships and avoid unhealthy relationships. Youth in Houston, located in Harris County, Texas, face additional challenges in creating stable relationships and home environments, as they face high rates of poverty, homelessness, and teen pregnancy. Homelessness among young adults in Harris County schools increased significantly following Hurricane Harvey, and school districts in Harris County saw surges of more than 22,000 students facing homelessness even months after Harvey hit (Texas Network of Youth Services 2018). Further, homeless youth, youth aging out of foster care, and LGBTQ youth are more vulnerable to falling victim to human trafficking, an issue that is highly prevalent in Houston.

Trauma-informed services are needed to improve self-sufficiency, economic stability, and healthy relationships among at-risk and homeless youth in Harris County, especially those living in areas with high numbers of single-family households, high poverty rates, low educational attainment, high teen pregnancy rates, high incidence of domestic violence, and high involvement with the (juvenile) justice system. AVANCE-Houston's Building Futures program (A-HBF) aims to facilitate successful transitions to adulthood for cohorts of at-risk and homeless youth by offering healthy relationship and marriage education through the *Survival Skills for Healthy Families (SSHF)* curriculum.

Developed by Family Wellness Associates, *SSHF* is an evidence-based curriculum delivered through a series of workshops that focus on communication skills, conflict resolution, knowledge of the benefits of marriage, stress and anger management, parenting skills, financial literacy, job and career advancement, and relationship skills to improve family and economic stability. To maximize participation, attendance, and convenience for youth and their parents, AVANCE will offer two curriculum delivery models: weekly workshops for youth that take place in targeted high-need schools and an intensive weekend retreat model co-attended by youth and parents.

AVANCE seeks to understand if participation in the A-HBF program is associated with improved outcomes among the target population of at-risk and homeless youth. Additionally, the evaluation will examine how and why participant-level characteristics such as relationship status, life status, and demographics are associated with greater or lesser benefit from A-HBF program participation. This research will provide insights about the *SSHF* curriculum and its effectiveness for the target population that can be used in the development of future programming efforts.

Table 1: Research Question Rationale

Research Question Topics	Existing Research	Contribution to the Evidence Base	Interest to the Program and/or Community
R1	Little empirical evidence exists in the field of HMRE to demonstrate the extent to which a skills-based curriculum can help at-risk and homeless youth build healthy partner relationship attitudes .	Determine whether offering a skills-based curriculum, in combination with family and career support services, enhances partner relationship attitudes among at-risk and homeless youth.	Inform practitioners about useful methods to consider when delivering skills-based curriculum to build healthy partner relationship attitudes among at-risk and homeless youth.
R2	Little empirical evidence exists in the field of HMRE to demonstrate the extent to which a skills-based curriculum can help at-risk and homeless youth build healthy sexual attitudes .	Determine whether offering a skills-based curriculum, in combination with family and career support services, enhances sexual attitudes among at-risk and homeless youth.	Inform practitioners about useful methods to consider when delivering skills-based curriculum to build healthy sexual attitudes among at-risk and homeless youth.
R3	Little empirical evidence exists in the field of HMRE to demonstrate the extent to which a skills-based curriculum can help at-risk and homeless youth build healthy partner relationship behavior .	Determine whether offering a skills-based curriculum, in combination with family and career support services, enhances partner relationship behavior among at-risk and homeless youth.	Inform practitioners about useful methods to consider when delivering skills-based curriculum to build healthy partner relationship behavior among at-risk and homeless youth.
R4	Little empirical evidence exists in the field of HMRE to demonstrate the extent to which a skills-based curriculum can help at-risk and homeless youth build healthy financial attitudes .	Determine whether offering a skills-based curriculum, in combination with family and career support services, enhances financial readiness among at-risk and homeless youth.	Inform practitioners about useful methods to consider when delivering skills-based curriculum to build healthy financial attitudes among at-risk and homeless youth.

R5	Little empirical evidence exists in the field of HMRE to demonstrate the extent to which a skills-based curriculum can help at-risk and homeless youth build healthy employment attitudes .	Determine whether offering a skills-based curriculum, in combination with family and career support services, enhances employment readiness among at-risk and homeless youth.	Inform practitioners about useful methods to consider when delivering skills-based curriculum to build healthy employment attitudes among at-risk and homeless youth.
-----------	--	--	--

B. Research question(s)

Research questions in this study are framed by a descriptive evaluation design to assess whether outcomes improve for at-risk and homeless youth after participating in the AVANCE-Houston Building Futures (A-HBF) Project. Primary outcomes will indicate whether behavior is improving over time for healthy relationships. Secondary benefits will indicate whether the attitudes that facilitate and reflect behavior for healthy family relationships and economic stability (financial and employment) are improving over time. Research questions that focus on primary and secondary outcomes for this study are presented below in Table 2.

Table 2: Outcome Research Questions

No	Research Question	Primary or Secondary Outcome?
R1	Do A-HBF participants report significantly healthier partner relationship attitudes after completing the SSHF curriculum in either a standard (weekly) or compressed (weekend retreat) workshop format and support services?	Secondary Outcome
R2	Do A-HBF participants report significantly healthier sexual attitudes after completing the SSHF curriculum in either a standard (weekly) or compressed (weekend retreat) workshop format and support services?	Secondary Outcome
R3	Do A-HBF participants report significantly healthier partner relationship behavior after completing the SSHF curriculum in either a standard (weekly) or compressed (weekend retreat) workshop format and support services?	Primary Outcome
R4	Do A-HBF participants report significantly healthier financial attitudes after completing the SSHF curriculum in either a standard (weekly) or compressed (weekend retreat) workshop format and support services?	Secondary Outcome
R5	Do A-HBF participants report significantly healthier employment attitudes after completing the SSHF curriculum in either a standard	Secondary Outcome

(weekly) or compressed (weekend retreat) workshop format and support services?

C. Relation to program logic model

Figure 1 in Appendix A presents a logic model to specify a theory of change for delivering A-HBF services. Service delivery processes specified in the model are linked to the desired outcomes for healthy relationships and economic readiness. Model specification incorporates a descriptive study design to conceptualize service delivery and the outcomes assessed for the A-HBF Project.

Service delivery processes: Key aspects of service delivery processes in the theory of change—goals, inputs, activities, and outputs—articulate the experiences that are designed to solve specific problems for those who agree to participate in the A-HBF Project. As a result, three broad service delivery goals are identified to maximize A-HBF Project participation benefits as explained below:

- **Goal 1 - Deliver *core curriculum* as primary services to A-HBF participants:** Candidates will understand that they receive *core curriculum* to develop healthy attitudes (partner relationship, sexual, financial, and employment) and skills to engage in healthy partner relationship behaviors, but only after receiving an orientation about the A-HBF Project and giving project staff informed consent to participate in study activities. Then, *SSHF* curriculum will be delivered as specified in the logic model.
- **Goal 2 - Deliver *support services* to A-HBF participants:** Candidates will understand that they receive *support services* based on their needs to further develop their skills to engage in healthy relationships and their financial and employment readiness, but only after receiving an orientation about the A-HBF Project and giving project staff informed consent to participate in study activities. Then, Family Coaches and Career Coaches will offer trainings and make referrals to promote further success for participants.
- **Goal 3 - Conduct Continuous Quality Improvement (CQI) to ensure full implementation of project services to participants:** Reports prepared and presented to the CQI Team by evaluators in each of the 5 steps in the CQI Process will use a series of performance indicators to track key outputs over time to identify any A-HBF services delivered to study groups that might fall short of the intended amounts to be offered (i.e., fidelity standards) and received (i.e., dosage thresholds) by them. The CQI Team will then work with project staff to develop and implement performance interventions to address any outputs that need improvement to ensure the services offered to and received by participants meet the intended amounts by the end of each program year.

Desired Outcomes: Outcomes specified in the logic model theorize the primary and secondary outcomes that are desired for participants after they complete A-HBF services. Secondary outcomes are the improved attitudes that indicate and reflect participant engagement in healthy partner relationship behaviors and capacity for future economic stability. Primary outcomes are the healthier behaviors exhibited by participants for partner relationships that ultimately define the participation benefits for the A-HBF Project. All outcomes specified in the logic model are theorized to be more positive for eligible at-risk and homeless youth after they complete primary services and support services.

D. Hypotheses

Table 3 below presents the hypotheses associated with the primary and secondary research questions for this descriptive study. Primary and secondary outcomes are reported on participant survey measures that are administered shortly after A-HBF enrollment and again one year later after study groups complete services (or should have completed them). Confirmatory hypotheses focus on the extent to which participants report improved attitudes (partner relationship, sexual, financial, and employment) and behaviors (partner relationship) after A-HBF participation.

Table 3: Hypothesized Results

Research Question	Hypothesized Result
R1	Participants will report healthier partner relationship attitudes after they complete primary services and support services in the A-HBF Project.
R2	Participants will report healthier sexual attitudes after they complete primary services and support services in the A-HBF Project.
R3	Participants will report healthier partner relationship behavior after they complete primary services and support services in the A-HBF Project.
R4	Participants will report healthier financial attitudes after they complete primary services and support services in the A-HBF Project.
R5	Participants will report healthier employment attitudes after they complete primary services and support services in the A-HBF Project.

II. Research Design and Staff

A. Research design

In this study, a descriptive study design will be used to determine if A-HBF participants benefit from the *Survival Skills for Healthy Families (SSHF)* curriculum. At-risk or homeless youth who agree to participate in the study will receive the *SSHF* curriculum through either a series of 7 in-school weekly workshops (14 hours) or an intensive weekend retreat co-attended by their parents (16 hours) followed two weeks later by a Reflections Workshop (2 hours). All program participants also receive support services delivered by Family Coaches and Career Coaches as needed.

Baseline data will be collected from participants shortly following study enrollment. Post-test data will be collected following curriculum completion, approximately 2-7 weeks following study enrollment depending on the curriculum delivery format. Follow-up data will be collected one year after study enrollment.

B. Methods to develop study groups

Because this is a descriptive evaluation, this subsection is not relevant.

C. Sample

The target population for this study is at-risk and homeless youth from high-need school districts in Harris County who are 14-18 years of age and enrolled in 9-12th grades. AVANCE will work with school districts, school boards, and individual schools to identify and recruit participants from the target population. The unit of analysis for this study is individual youth. See Appendix D for anticipated sample flow and attrition rates.

Power analysis:

The analysis of survey data will address the primary and secondary research questions with findings derived from running a linear regression model that quantifies the potential benefits of Building Futures Program participation and outcomes as well as the relationship of participant characteristics to Building Futures Program benefits. Benefits are quantified by specifying a model that compares the relative influences of participant characteristics as predictor that is regressed against a series of dependent variables (e.g., outcomes specified in the logic model). Given the predicted sample size as described in the appended logic model, the following calculations regarding power and effect size can be made.

	Participant Responses	Minimum Detectable Effect Size
Post-test	1105	0.017
Follow-up	774	0.023

These power analyses assume an Alpha Level of 0.05 with a two-tailed test and power level set at 0.80 (1 – Beta). The estimated effect sizes are all small effects or nearly small effects that would be detected, based on best practices outlined by Cohen (1988) of small effect sizes <0.02 and medium effect sizes <0.15. With these analyses, the proposed research design is demonstrated to measure large, medium, and small changes in participants' responses.

Table 4: Methods to Promote Sufficient Program Participation

What methods will you use to ensure sufficient sample is recruited, enrolls, and participates in the program?	AVANCE will work with schools and their community partners to recruit program participants, and AVANCE will provide incentives for program retention and completion. The CQI process will address issues regarding program recruitment and enrollment to ensure targets are met.
Who will be responsible for recruiting the evaluation sample?	The evaluation sample will not differ from the program population, in that all participants will be invited to participate in the evaluation. Enrollment into the evaluation will be conducted by the CQI Data Manager who will conduct the informed consent process and proctor the baseline data collection efforts.

Please describe any incentives to be offered for program participation and/or completion and/or data collection and/or participation in the evaluation.

Program Participation – AVANCE will provide a series of incentives for program retention (promotional items) and completion (\$75 gift card).

Evaluation Participation – No incentives will be used for the first two data collections- baseline and post-test, while participants are beginning or still engaged in services. A \$50 incentive will be used for the 1-year follow-up survey and will be provided in the form of a Walmart gift card.

D. Lead staff

See Appendix B for CVs of lead evaluation staff.

Table 5: Lead Evaluation Staff

Name	Organization	Role in the Evaluation
[name]	Midwest Evaluation and Research	Principal Investigator
[name]	Midwest Evaluation and Research	Lead Evaluation Consultant
[name], MA	Midwest Evaluation and Research	Evaluation Project Manager
[name]	Midwest Evaluation and Research	CQI Data Manager

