Partner Relationship Attitudes	9 items: levels of agreement with relationship beliefs (categories, 4-point); 3 items: likelihood of key relationship beliefs (categories, 5-point scale)	nFORM Healthy Marriage Youth Program Survey (A1.a-i; A2.a-c)	nFORM
Sexual Attitudes	7 items: levels of agreement with key sexual attitudes (categories, 4-point scale)	nFORM Healthy Marriage Youth Program Survey (B1.a-g)	nFORM
Partner Relationship Behavior	5 items: levels of reported skill with key relationship behaviors (categories, 4-point scale); 6 items: frequency engage in key relationship behaviors (categories, 5-point scale)	nFORM Healthy Marriage Youth Program Survey (C1b.a-e; C3.a-f)	nFORM
Financial Attitudes	4 items: levels of agreement with key financial	OLLE (Online Local	In appendix D of: Jurkiewicz, T. & Friedman, L. (2020). Impact Evaluation of The TYRO

	attitudes (categories, 7-point scale)	Evaluation) Survey	Champion Dads Project in Dallas, Texas: Final Impact Evaluation Report for Anthem Strong Families. Midwest Evaluation and Research.
Employment Attitudes	4 items: levels of agreement with key employment attitudes (categories, 7-point scale)	OLLE (Online Local Evaluation) Survey	In appendix D of: Jurkiewicz, T. & Friedman, L. (2020). Impact Evaluation of The TYRO Champion Dads Project in Dallas, Texas: Final Impact Evaluation Report for Anthem Strong Families. Midwest Evaluation and Research.

Consent:

Because the planned evaluation involves human subjects, AVANCE understands program implementation requires both IRB approval and participant informed consent. MER has an established relationship with Solutions IRB, having secured more than 14 IRB approvals and renewals for evaluations it has conducted during the past four years. IRB clearance will be submitted for approval and obtained during the planning period.

Each school location will have a signed letter of agreement to be included in this project. This must be filed with the IRB during the application process. Any school locations that are later recruited into the study will result in MER submitting amendments to the IRB to include these schools as research sites, and the additional school's letter will be included in the project.

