## IV. Data Analysis

### A. Data analysis

To examine the research questions, a repeated measures design will be used. The within-subjects factor will be the time of measurement (pre-survey and 12-month follow-up survey), and the between-subjects factor will be the format of the SSHF curriculum (standard or compressed) and support services.

Descriptive statistics will be computed to summarize the demographic variables and the variables of interest. Shapiro-Wilk tests will be conducted to assess the normality of the data. If the data are not normally distributed, appropriate transformations will be applied, or nonparametric tests will be used. To examine the first research question, a repeated measures analysis of variance (ANOVA) will be conducted with partner relationship attitudes as the dependent variable. The between-subjects factor will be the format of the SSHF curriculum, and the within-subjects factor will be time of measurement. If significant main effects or interactions are found, post hoc tests (e.g., Bonferroni) will be conducted to examine the pairwise comparisons.

The same approach will be used for the remaining research questions, with sexual attitudes, partner relationship behavior, financial attitudes, and employment attitudes as dependent variables. The level of statistical significance will be set at  $p < 0.05$ . Effect sizes will be reported using partial eta-squared ( $\eta^2$ ), which provides an estimate of the proportion of variance in the dependent variable accounted for by each factor in the ANOVA.

To examine the reliability of the scales, Cronbach's alpha will be computed for each construct. A value of 0.70 or higher will indicate acceptable reliability. To examine the validity of the scales, confirmatory factor analysis (CFA) will be conducted to test the hypothesized factor structure of each construct. If the hypothesized factor structure does not fit the data well, exploratory factor analysis (EFA) will be conducted to identify the underlying factor structure. Missing data will be handled using multiple imputation techniques to minimize bias and increase power. Overall, this study will use a repeated measures design with ANOVA to examine the effects of the SSHF curriculum on various domains of relationship and personal functioning and will use reliability and validity analyses to ensure the psychometric properties of the measures.

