### Model Specification to Predict Outcomes With Dosage

Construct by Outcome	Dependent Variables (follow-up)	Response Codes for Dependent Variables	Dependent Variable Type	Independent Variables
Primary outcome:				
Partner Relationship Behavior: 6 scaled items	DISAG_BE_FU	1 = none of the time to 5 = all of the time	Continuous	Dosage of curriculum; co-variates (using pre-survey scores)
5 scaled items	REL_BE_FU	1 = I am extremely good at this to 4 = I am extremely bad at this		
Secondary outcomes:				
Partner Relationship Attitudes: 9 scaled items	PARTREL_ATT_FU	1 = strongly agree to 4 = strongly disagree	Continuous	Dosage of curriculum; co-variates (using pre-survey scores)
3 scaled items	PARTREL_FUT_ATT_FU	1 = almost no chance to 5 = almost certain		
Sexual Attitudes: 7 scaled items	SEX_ATT_FU	1 = strongly agree to 4 = strongly disagree		
Financial Attitudes: 4 scaled items	FIN_ATT_FU	1 = strongly disagree to 7 = strongly agree		
Employment Attitudes 4 scaled items	EMP_ATT_FU	1 = strongly disagree to 7 = strongly agree		

Step 4 – run the linear regression model: Procedures to run the linear regression model are influenced by dependent variable types. Standard regression is necessary to model the influence of curriculum dosage on continuous dependent variables, such as when participants respond to

---

multiple items in a scaled construct by indicating levels of agreement with statements about key partner relationship attitudes.

Step 5 – interpret model results: Model results demonstrate the benefits of A-HBF participation whenever dosage variables predict more positive primary and secondary outcomes for a construct. For primary outcomes, benefits of receiving *SSHf* curriculum confirm hypotheses when respondents with higher levels of participation more frequently report ( $p < .05$ ):

1. Healthy partner relationship behavior

For secondary outcomes, benefits of receiving *SSHf* curriculum confirm hypotheses when respondents with higher levels of participation more frequently report ( $p < .05$ ):

2. More positive attitudes about partner relationships
3. More positive attitudes about sexual relationships
4. More positive attitudes about financial readiness
5. More positive attitudes about job readiness

---

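### Youth are recruited through schools and taught in groups, but the planned tests and the power table treat them as independent; the time and format tests are the most exposed

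*Protocol*

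**What the plan says.** Protocol section I.A describes a programme for "cohorts of at-risk and homeless youth", delivered through "weekly workshops for youth that take place in targeted high-need schools and an intensive weekend retreat model co-attended by youth and parents". Section II.C says that "AVANCE will work with school districts, school boards, and individual schools to identify and recruit participants from the target population", and then that "The unit of analysis for this study is individual youth". Under Consent in section III.A, schools are separate research sites: "Each school location will have a signed letter of agreement to be included in this project", and further schools may join by amendment.

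For the main analysis, SAP section IV.A specifies a repeated-measures ANOVA on the pre-survey and the 12-month survey: "The between-subjects factor will be the format of the SSHF curriculum, and the within-subjects factor will be time of measurement". The dosage analysis regresses change on hours attended, adjusting for format, support services and selected demographics. The model specification that follows adds pre-survey scores and says that "Standard regression is necessary to model the influence of curriculum dosage on continuous dependent variables". The named regression checks cover normality, constant variance, linearity and collinearity, but not independence.

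The power calculations in protocol section II.C "assume an Alpha Level of 0.05 with a two-tailed test and power level set at 0.80". They give minimum detectable effects of 0.017 (1105 responses at post-test) and 0.023 (774 at follow-up). They mention no ICC, group size or design effect.

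**The concern.** Youth in one workshop series or retreat share sessions and peers, and they complete the baseline and post-test surveys around those sessions. The outcomes are attitudes and relationship behaviour, on which peers may influence one another. Some correlation of change within a group is therefore plausible. The repeated-measures term deals with correlation within one youth over time. It does nothing about correlation between youth in the same group.

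The protocol calls its hypotheses confirmatory, and the SAP decides them at p < 0.05. If groups share part of their change, the time test for all five research questions rejects too often. So does the test of format, which is constant within a delivery group. The protocol's claim that the design can measure even small changes also depends on independence.

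**Working it through.** **Inputs from the documents:** 1105 responses at post-test, 774 at follow-up, two-sided alpha 0.05, power 0.80. **Assumed, because the documents give neither:** m, the number of analysed youth per group, and ICC, the correlation between two youth in the same group. For the time and format-by-time tests the relevant ICC is that of change scores.

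**1. The plan's own figures.** The protocol's benchmarks for small (0.02) and medium (0.15) point to f-squared in linear regression. Solving the noncentral F test (noncentrality = f-squared × N) for power 0.80 with every response independent:
- 0.017 at N = 1105 is matched with 14 or 15 predictors (0.0168, 0.0172).
- 0.023 at N = 774 is matched with 12 or 13 predictors (0.0227, 0.0234).

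The number of predictors is not stated, and no single number gives both figures. The nearest, 13, gives 0.0163 and 0.0234. The stated values are thus the size expected from a calculation with no design effect, but they cannot be reproduced exactly.

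**2. Effect of clustering on the time and format tests.**
- Design effect: DEFF = 1 + (m − 1) × ICC
- Standard error ratio: √DEFF
- Effective N = N / DEFF
- True level of a nominal 5% test = 2 × [1 − Φ(1.96 / √DEFF)]

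Example with m = 20 and ICC = 0.05: DEFF = 1 + 19 × 0.05 = 1.95; √1.95 = 1.396; 1.96 / 1.396 = 1.404; true level 0.160.

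The main analysis uses the 12-month survey. A group of 20 at post-test becomes 20 × 774/1105 ≈ 14 at follow-up, so m = 14 is the low case.

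| m | ICC | DEFF | SE ratio | Effective N of 774 | True level |
|---|---|---|---|---|---|
| 14 | 0.01 | 1.13 | 1.06 | 685 | 6.5% |
| 14 | 0.02 | 1.26 | 1.12 | 614 | 8.1% |
| 14 | 0.05 | 1.65 | 1.28 | 469 | 12.7% |
| 20 | 0.01 | 1.19 | 1.09 | 650 | 7.2% |
| 20 | 0.02 | 1.38 | 1.17 | 561 | 9.5% |
| 20 | 0.05 | 1.95 | 1.40 | 397 | 16.0% |
| 30 | 0.01 | 1.29 | 1.14 | 600 | 8.4% |
| 30 | 0.02 | 1.58 | 1.26 | 490 | 11.9% |
| 30 | 0.05 | 2.45 | 1.57 | 316 | 21.0% |

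A simulation (4,000 runs, about 774 youth, format constant within group) agrees. For m = 20 and ICC 0.05 it gives 16.7% for time and 16.3% for format.

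**3. Dosage test, same simulation.** With m = 20 and outcome ICC 0.05, the true level is 5.3% if hours vary only within groups, and 8.4% if hours themselves have an assumed ICC of 0.3. With m = 30 and outcome ICC 0.05, the two figures are 5.4% and 9.7%.

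**4. Detectable effects.** With 13 predictors assumed and N replaced by N / DEFF, post-test / follow-up values are:
- m = 20, ICC 0.02: 0.023 / 0.033
- m = 20, ICC 0.05: 0.032 / 0.046
- m = 30, ICC 0.05: 0.041 / 0.059

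The stated values are 0.017 / 0.023. The full design effect applies to predictors that are constant within a group, so for a regression with individual-level predictors these figures are an upper bound.

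**The case against.** The strongest reply is that the size of the problem is unknown. Group size, number of schools and ICC are all absent. Stable differences between schools cancel in a within-person contrast, so the ICC of change may be well below that of raw scores; near zero, the planned tests are close to correct. This stands. A reader might infer that the p-values are certain to be too small. The documents support only the conditional statement.

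A reader might also infer that dosage is among the most exposed tests, which would matter because Step 5 of the SAP confirms hypotheses on the dosage coefficient. The documents do not support that. The model adjusts for format, which absorbs the planned difference in hours (14 for weekly workshops; 16 plus 2 for the retreat). The simulated error stays near 5% unless attendance itself clusters.

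Three further points stand:
- No passage says that schools determine format. It is fixed only by the group a youth attends. Format is also not one of the research questions, which ask about change in either format.
- The SAP text reports p-values and partial eta-squared. It plans no confidence intervals, so a claim that the intervals would be too narrow has no basis.
- Taking the individual as the unit of analysis is not an error in itself. It is compatible with cluster-adjusted inference.

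The regression procedure in the supplied SAP begins at Step 4 and its covariates are not listed in full, so the finding covers the supplied text. The ANOVA's factors, however, are stated explicitly. The descriptive label does not answer the concern either, because the hypotheses are called confirmatory and are tested at p < 0.05.

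**Conclusion.** The concern holds in conditional form. Followed as written, the supplied plan ignores any correlation between youth in the same school or delivery cohort. If change is positively correlated within groups, the standard errors for time are too small, and so are those for format. With 14 to 30 analysed youth per group and a change-score ICC of 0.01 to 0.05, they should be about 1.06 to 1.57 times larger, and a nominal 5% test has a true level of about 6.5% to 21%. The main effect of format depends on the ICC of the score averaged over the two surveys, for which the same formula holds. Under these assumptions the stated detectable effects are optimistic. Dosage is a lesser issue that depends on how far hours cluster. All sizes rest on assumed group sizes and ICCs; the documents fix neither.

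**What to change.** 1. Record a school and a delivery-cohort identifier for every participant.
2. Replace the ANOVA with a linear mixed model that has a person random intercept, and cohort and school random effects on both level and change over time. A school intercept alone would not protect the time effect against change shared by a school. Use a cross-classified structure if retreats mix schools.
3. Give the dosage regression, which has one record per youth, cohort and school random effects.
4. Alternatively, keep the planned models and use cluster-robust standard errors with a small-sample correction, clustering on school and delivery cohort (two-way if retreats mix schools). Clustering on school alone would miss mixed retreat groups. With few schools, even corrected errors may be unreliable, so state the expected number of schools and cohorts.
5. Carry the same structure into the multiple imputation.
6. Restate the minimum detectable effects over a stated range of ICC and cluster size, and give the number of predictors.

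The cost is revised SAP wording and two identifiers that programme staff should already hold. The price in results is larger p-values and less favourable stated detectable effects. If the estimated ICCs prove negligible, little is lost.
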